8.3.3. Longitudinal Changes in anti-COVID-19 Antibody Responses

Longitudinal changes in anti-COVID-19 antibody responses will be analyzed from Week 0 to Weeks 4, 12, 24, 36, and 48 and will be summarized over time by study visit using descriptive statistics. This endpoint will not be evaluated in preliminary analyses. Additional analysis details will be provided in subsequent versions of the SAP.

8.3.4. Longitudinal Changes in Neutralization and Pseudo Neutralization Assays

Longitudinal changes in neutralization and pseudo neutralization assays will be assessed from Week 0 to Weeks 4, 12, 24, 36, and 48 and will be summarized by study visit using descriptive statistics. This endpoint will not be evaluated in preliminary analyses. Additional analysis details will be provided in subsequent versions of the SAP.

8.3.5. Changes in Diseases Activity using CGI-C

Changes in disease activity after receipt of additional doses of COVID-19 vaccine will be assessed as measured by the CGI-C. In preliminary analyses, the change in CGI-C from Week 0 to Week 4 will be summarized in each study population using descriptive statistics. Analysis details will be provided in subsequent versions of the SAP.

8.3.6. Changes in Diseases Activity using PGA

Changes in disease activity after receipt of additional doses of COVID-19 vaccine will be assessed as measured by the PGA. This endpoint will not be evaluated in preliminary analyses. Analysis details will be provided in subsequent versions of the SAP.

8.3.7. Changes in Disease Activity as Measured by Disease-Specific Assessments

Longitudinal changes in disease activity will not be evaluated in preliminary analyses. The proportion of participants who meet the definition for disease-specific flares by Week 4 will be summarized in preliminary analyses.

8.3.7.1. H-SLEDAI and SELENA-SLEDAI Flare Index

Disease activity for SLE participants will be measured by the (H-SLEDAI and SELENA-SLEDAI Flare Index for SLE. Analysis details will be provided in subsequent versions of the SAP.

8.3.7.2. DAS28-CRP

Disease activity for RA participants will be measured by the DAS28-CRP for RA. Analysis details will be provided in subsequent versions of the SAP.

8.3.7.3. Flare assessment for SSc

Disease activity for SSc participants will be measured using the flare assessment for SSc (including patient-reported flare assessment). Analysis details will be provided in subsequent versions of the SAP.

8.3.7.4. PDAI

Disease activity for pemphigus participants will be measured using the PDAI for pemphigus. Analysis details will be provided in subsequent versions of the SAP.

8.3.7.5. Physician-assessed relapse for MS

Disease activity for MS participants will be measured using the physician-assessed relapse for MS. Analysis details will be provided in subsequent versions of the SAP.

8.3.7.6. JADAS-10

Disease activity for JIA participants will be measured using the JADAS-10 for polyarthritis, enthesitis related to JIA, oligoarthritis, and psoriatic arthritis. Analysis details will be provided in subsequent versions of the SAP.

8.3.7.7. PASI

Disease activity for JIA participants will also be measured using the PASI for psoriatic arthritis. Analysis details will be provided in subsequent versions of the SAP.

8.3.7.8. SLEDAI-2K and Childhood-onset SLE Criteria for Global Flare

Disease activity for pediatric SLE will be measured using the SLEDAI-2K and Childhood-onset SLE Criteria for Global Flare [1] for pediatric SLE. Analysis details will be provided in subsequent versions of the SAP.

8.3.7.9. CMAS

Disease activity for JDM will be measured using the CMAS for JDM. Analysis details will be provided in subsequent versions of the SAP.

8.3.7.10. JDM DAS

Disease activity for JDM will be measured using the JDM DAS for JDM. Analysis details will be provided in subsequent versions of the SAP.

8.3.7.11. Physician-assessed relapse for POMS

Disease activity for POMS will be measured using the physician-assessed relapse for MS for POMS. Analysis details will be provided in subsequent versions of the SAP.

8.3.8. Changes in Patient-reported Outcomes

8.3.8.1. PROMIS 29

Changes in the PROMIS 29 will be assessed in the adult population. Analysis details will be provided in subsequent versions of the SAP.

8.3.8.2. PedsQL

Changes in the PedsQL will be assessed in the pediatric population. Analysis details will be provided in subsequent versions of the SAP.

8.3.8.3. PtGA

Changes in the PtGA will be assessed in the adult and pediatric populations. Analysis details will be provided in subsequent versions of the SAP.

8.3.8.4. PGI-C

Changes in the PGI-C will be assessed in the adult and pediatric populations. Analysis details will be provided in subsequent versions of the SAP.

8.4. Other Endpoints

Analysis details will be provided in subsequent versions of the SAP.

8.5. Examination of Subgroups

Analysis details will be provided in subsequent versions of the SAP.

9. SAFETY EVALUATION

9.1. Overview of Safety Analysis Methods

All safety analyses will be carried out using the safety sample defined in Section 5 unless otherwise noted. Missing safety information will not be imputed. These analyses will not be stratified by site.

9.2. Adverse Events

For this study, solicited AEs are predefined local and systemic events for which the participants will be specifically questioned, and which will be noted by these participants. An AE is considered “unsolicited” when it is collected through an open-ended question and is not specified as a solicited AE. An MAAE is defined as a hospitalization, emergency room visit, or an otherwise unscheduled visit to or from medical personnel for any reason; and considered related to study vaccine. A NOCMC is defined as any new ICD diagnosis (per current International Statistical Classification of Diseases and Related Health Problems) that is applied to the study participant during the course of the study, after receipt of the vaccine, that is expected to continue for at least 3 months and requires continued health care intervention. An AE is considered “serious” if, in the view of either the investigator or Sponsor (DAIT/NIAID), it results in any of the following outcomes: death, life-threatening, hospitalization, persistent or significant incapacity, congenital anomaly or birth defect, or is considered an important medical event. See protocol Section 12.2 for more details on AE definitions.

The collection periods and reporting for AEs are as follows:

- Solicited AEs (all grades) will be collected from Day 1 (vaccine administration) through 7 days post study vaccination using the MyOwnMed vaccine reaction diary.
 - Investigators are responsible for reporting solicited AEs in the electronic data capture system (EDC) in the following special cases:
 - If a solicited AE is also an SAE or MAAE must be entered in EDC to capture additional information about the event.
 - If a solicited AE, previously reported in MyOwnMed, is found to be ongoing at Day 7 (post vaccination), the solicited AE must be entered in EDC so it can be followed to resolution, with or without sequelae.
 - Unsolicited AEs (unrelated to reactogenicity) that are entered into the Vaccine Reaction Diary and are also identified during the Week 1 visit are to be reported in EDC
 - Unsolicited AEs will be collected as follows and reported in EDC:
 - Any unsolicited AEs that are Grade 3 or higher will be collected from randomization/allocation through vaccination administration.
 - All unsolicited AEs (all grades) will be collected from Day 1 through Day 28.

- Any flares of a secondary autoimmune disease will be reported as an unsolicited AE (all grades) and will be collected from Day 1 through the end of the participant's study participation.
- SAEs, MAAEs, and NOCMCs will be collected from Day 1 through the end of the participant's study participation, regardless of the National Cancer Institute's (NCI's) Common Toxicity Criteria for Adverse Events (CTCAE) grade, and reported in EDC.
- COVID-19 diagnoses (all grades) confirmed by molecular COVID-19 testing will be collected from Day 1 through the end of the participant's study participation and reported in EDC.

All AEs will be classified by system organ class (SOC) and preferred term, according to a standardized thesaurus (Medical Dictionary for Regulatory Activities [MedDRA] version 24.0).

Grading criteria are defined as follows:

- Solicited AEs: Participants will grade solicited AEs using a 0-3 (no symptom, mild, moderate, and severe) participant symptom rating scale as outlined in the Vaccine Reaction Diary instructions.
- Allergic reactions: The investigator will grade severity of systemic allergic reactions on a scale of 1 to 5 according to criteria set forth in the Consortium of Food Allergy Research (CoFAR) Grading Scale modified for use in adults only (See Protocol Section 20.2 CoFAR Grading Scale for Systemic Allergic Reactions Version 3.0).
- Liver Function Abnormalities: Liver function abnormalities will be graded using alternative criteria, which are based on the NCI-CTCAE version 4.0, and are defined relative to the upper limit of normal (ULN) as defined in Protocol Section 12.3.1 *Grading Criteria*.
- All other events: The study site will grade the severity of all other AEs experienced by the study participants according to the criteria set forth in the NCI-CTCAE version 5.0 as deemed appropriate for the 5 adult autoimmune diseases and 4 pediatric autoimmune diseases, and use of background IS medications of interest in this trial.

If the start date of an AE is incomplete or missing, it will be assumed to have occurred on or after the first dose of investigational product, except if an incomplete date (e.g., month and year) clearly indicates that the event started prior to treatment

If a subject experiences the same AE on multiple occasions, the event will be counted once for each occurrence when reporting the number of AEs. When reporting the number of subjects experiencing the events, a subject will only be counted once if they experience at least one event within the particular SOC or preferred term. Percentages will be based on the number of subjects in the safety population. The tabular summaries will be sorted by descending frequency by SOC and preferred term (PT) in the treatment group arm.

Summary tables will be reported for treatment emergent adverse events unless otherwise indicated. An overall summary table will include:

- Total number of events, and number and percentage of subjects experiencing at least one event for the following categories:
 - AEs
 - SAEs
 - AEs related to study vaccine
 - AE leading to study vaccine discontinuation
 - AE leading to death
 - MAAEs
 - NOCMCs
 - SARS-CoV-2 infections
 - Solicited Adverse Events
 - AEs by severity

AEs classified by MedDRA SOC and preferred term will be summarized for each treatment group for each of the following:

- All AEs
- All Related AEs
- All SAEs
- All AEs leading to study drug discontinuation
- AEs by severity
- AEs by relationship to study drug

Listings of all AEs, MAAEs, and NOCMCs will be provided for the safety population.

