8.1.3 Baseline (Week 0/Day 1) Visit

Eligible participants who meet all inclusion criteria and none of the exclusion criteria will proceed with visits and assessments according to Section 20.1 Schedule of Events. Eligible participants will be assessed for disease activity and SARS-CoV-2 infection at the Baseline/Week 0 visit, prior to receipt of an additional homologous vaccine dose. Prior to administering the additional homologous vaccine dose at the Baseline visit, the site will confirm the participant meets vaccine eligibility per the criteria below:

- No increase to the permitted concomitant medications in participants in Cohorts A and B between Randomization and Baseline/Week 0.
- No B-cell depletion infusions or changes in permitted concomitant medications in participants in Cohort C between allocation and Baseline/Week 0.
- No clinically active disease (including myocarditis or pericarditis) at Baseline/Week 0 resulting in an increase/addition of IS medications. For participants with MS, no suggestion of a MS relapse per the investigator.
- No active myocarditis or pericarditis based on review of clinical symptoms.
- No positive molecular COVID-19 test at Baseline/Week 0.
- No increase in oral, intramuscular, or intravenous steroids within 14 days of Baseline/Week 0.

If the vaccine cannot be administered at the Baseline/Week 0 visit, it must be administered during the following 2-3 days. Vaccine eligibility will be confirmed prior to administration of the vaccine. **Administration of the additional homologous vaccine dose must occur within 28 days of the Screening visit.**

If a participant is not eligible to receive the additional homologous vaccine dose at Baseline/Week 0, he/she will be terminated from the study. The participant may rescreen under a new participant ID after 30 days from the determination of vaccine ineligibility. Participants who were randomized to withhold cohort-defining IS medications before the Baseline visit and who are not eligible to receive an additional homologous vaccine dose at that visit, may restart their IS medications immediately. The participant will be replaced.

See Section 8.1.4 Study Procedures and Assessments for more information on individual clinical and research assessments.

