11.4 Follow-up after Early Study Withdrawal

Participants who prematurely withdraw (without withdrawing consent) or who are withdrawn may be asked to complete a final phone visit to assess any AEs and concomitant medications as applicable depending on when they are withdrawn relative to the visit schedule. Participants who are withdrawn from the study prior to receipt of study treatment will not be followed after their last completed study visit. Monitoring of a pregnant participant will continue until the conclusion of the pregnancy.

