12.4 Collection and Recording of Adverse Events

12.4.1 Collection Period For All Cohorts

For this study, the timelines below apply after each study-administered vaccine:

- Solicited AEs (all grades) will be collected from Day 1 (vaccine administration) through 7 days post study vaccination.
- Unsolicited AEs will be collected as follows:
 - Any unsolicited AEs that are Grade 3 or higher will be collected from randomization/allocation through vaccination administration.
 - All unsolicited AEs (all grades) will be collected from Day 1 through Day 28.

- Any flares of a secondary autoimmune disease will be reported as an unsolicited AE (all grades) and will be collected from Day 1 through the end of the participant's study participation.
- AESIs will be collected as follows:
 - Pericarditis/myocarditis events will be collected in all treatment arms. NCI-CTCAE Grade 2 or higher myocarditis and pericarditis events from Day 1 through the end of the participant's study participation.
 - New onset of pIMDs will only be collected in arms where the Sanofi-GSK COVID-19 Vaccine is administered. All grades will be collected from Day 1 through the end of the participant's study participation.
- SAEs, MAAEs, and NOCMCs will be collected from Day 1 through the end of the participant's study participation, regardless of NCI-CTCAE grade.
- COVID-19 diagnoses (all grades) confirmed by molecular COVID-19 testing will be collected from Day 1 through the end of the participant's study participation.

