5. ANALYSIS SAMPLES

Analysis samples for ACV01 for each study stage (Stage 1, Stage 2) and age group (Adult, Pediatric) will be defined as follows:

- **Vaccinated population:** will be defined as all participants who are randomized or allocated and receive study vaccine in the study. For all endpoints, participants will be evaluated by the actual vaccine received. In Cohorts A and B, participants will be analyzed in subgroups defined by randomized assignment to continue or withhold IS medications in the primary analysis.
- **Per protocol populations:** will be defined as the subgroup of participants in the vaccinated population who adhere to the treatment plan for IS medications defined in Section 7.1.1 Protocol-mandated Medications and have no major protocol deviations or ineligible entry criteria that would impact the vaccine response assessment at Week 4.
- **Safety population:** will be defined as all participants who initiate the treatment plan for IS medications or receive an additional dose of vaccine.

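### Safety percentages are taken over a population that can include people who were never vaccinated, so per-dose event rates are understated

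*SAP*

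**What the plan says.** SAP 5 (and Protocol 13.4.1 in the same terms) defines the safety population as "all participants who initiate the treatment plan for IS medications or receive an additional dose of vaccine". Vaccination is one route in; starting the IS plan is another. SAP 9.1 makes this population the default: "All safety analyses will be carried out using the safety sample defined in Section 5 unless otherwise noted". SAP 9.2 then fixes the denominator: "Percentages will be based on the number of subjects in the safety population". Neither SAP 9.2.1 on solicited events nor SAP 9.3 on serious events sets a different one.

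Collection starts later than entry to that population:

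- Solicited events, SAP 9.2: "Solicited AEs (all grades) will be collected from Day 1 (vaccine administration) through 7 days post study vaccination".
- Serious events, medically attended events and new chronic conditions, Protocol 12.4.1: "SAEs, MAAEs, and NOCMCs will be collected from Day 1 through the end of the participant's study participation". COVID-19 diagnoses also start at Day 1.
- The only earlier collection is of unsolicited events of Grade 3 or higher, from randomization or allocation up to vaccination.

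The plan foresees people who start a hold and are not vaccinated. Protocol 7.1.1 starts the hold 3 days (MMF/MPA) or at least 7 days (MTX) before the dose. Protocol 8.1.3 checks vaccine eligibility at Baseline and covers participants who withheld medication and then fail that check. Under Protocol 11.3, unvaccinated Stage 1 and newly recruited Stage 2 participants are withdrawn, do not count toward accrual and are replaced. Protocol 11.4 adds: "Participants who are withdrawn from the study prior to receipt of study treatment will not be followed after their last completed study visit". Unvaccinated Stage 2 rollovers instead return to their previous schedule (Protocol 8.2.4 and 8.4.4).

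**The concern.** The proportions of participants with vaccine-related events, SAEs, MAAEs, NOCMCs and SARS-CoV-2 infection are a named secondary endpoint (Protocol 3.3). The question behind them is what follows an additional dose. A rate per dose needs recipients of the dose in the denominator. Here the denominator can also hold people who received none and for whom most of the listed events are not collected, or cannot occur by definition. The reported percentage then falls below the rate among vaccinated participants. For a safety summary, that is the non-conservative direction.

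**Working it through.** The documents state no safety rate, no size for the safety population and no expected number of unvaccinated participants, so there is no figure of the plan's own to reproduce. The check has two parts.

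**1. Can a never-vaccinated participant enter the numerator?**

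- Solicited reaction: no. Collection begins at vaccine administration, and the diary covers the 7 days after the dose.
- MAAE: no. The definition requires a relation to study vaccine (SAP 9.2; Protocol 12.2.4).
- NOCMC: no. The diagnosis must follow receipt of vaccine (SAP 9.2; Protocol 12.2.3).
- SAE and COVID-19 diagnosis: not collected before Day 1. Stage 1 and newly recruited Stage 2 participants are not followed after withdrawal. This leaves little room for a contribution, but it is a collection rule and not a definition.
- Unsolicited event of Grade 3 or higher before vaccination: collected. SAP 9.2 limits the tables to treatment-emergent events unless otherwise indicated and does not define that term, so such an event would probably be left out of the tables.

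Populations are defined by stage. On the written definition, a rollover who starts the Stage 2 hold and is not vaccinated enters the Stage 2 denominator without a Stage 2 dose.

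**2. Size of the dilution**

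Inputs:

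- V, vaccinated per arm: up to 60 in Adult Stage 1, up to 80 elsewhere (Protocol 3.5). Because the unvaccinated are replaced, u comes on top of V.
- u, in the safety population but never vaccinated: **assumed**.
- r, true rate among the vaccinated: **assumed**, 70% for a common reaction. A 5% rate is shown for a rarer event; applied to SAEs, it also assumes that no SAE is recorded in the unvaccinated.

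Formula: reported rate = r × V/(V+u).

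| V | u | V/(V+u) | 70% is reported as | 5% is reported as |
|---|---|---|---|---|
| 60 | 0 | 1.000 | 70.0% | 5.00% |
| 60 | 1 | 60/61 = 0.984 | 68.9% | 4.92% |
| 60 | 3 | 60/63 = 0.952 | 66.7% | 4.76% |
| 60 | 7 | 60/67 = 0.896 | 62.7% | 4.48% |
| 80 | 2 | 80/82 = 0.976 | 68.3% | 4.88% |
| 80 | 9 | 80/89 = 0.899 | 62.9% | 4.49% |

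With vaccinated participants as the denominator, the factor is 1 whatever u is.

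**The case against.** The strongest defence is that the broad population has a purpose. The hold is a study intervention with its own risk of flare (Protocol 5.3.1), so people who start it should appear somewhere in the safety reporting. That stands, and it supports a separate table for the period before vaccination. It does not support the same denominator for reactions to a dose.

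The consequences are also limited. Safety proportions are descriptive (Protocol 13.4.4). SAP 6.1 reports who was not vaccinated and why, and SAP 7.3 reports vaccine receipt by arm, so a careful reader could rebuild the rates. The ad hoc DSMB triggers in Protocol 12.8.2.2 do not use these percentages. All of this stands as mitigation, but the published percentages would still be the diluted ones.

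A reader might go further and infer that dilution is greatest in the withhold arms, so that withholding looks safer. The documents do not support this. Continuing and withholding are both IS treatment plans (Protocol 3.1.1.1), the continue plan covers the same days before the dose (Protocol 7.1.1), and the Baseline eligibility checks apply to both. What it means to initiate the plan is not defined for continue arms, nor for Cohorts C and F. With V = 60 and a true 70% in both arms:

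- only a hold counts, u = 7 against 0: 62.7% against 70.0%;
- both plans count, u = 7 in each: 62.7% in both;
- both plans count, u = 7 against 3: 62.7% against 66.7%.

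The gap depends on a definition and on counts that the plan does not give. In Stage 2 there is no continue arm for Cohorts D and E to be compared with, and Cohort F participants on MMF/MPA or MTX also hold.

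Two other inferences go too far. One is that a vaccinated participant with no diary is counted as having no reaction: SAP 9.1 says that missing safety data are not imputed, and no rule covers an absent diary, so the handling is unspecified. The other is that rescreened people are counted twice. Protocol 8.1.3 says "The participant may rescreen under a new participant ID after 30 days from the determination of vaccine ineligibility", but nothing says whether the two records will be linked.

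**Conclusion.** The point holds as a denominator error whose direction is known and whose size is not. As written, the SAP understates solicited reaction, MAAE and NOCMC rates by the factor V/(V+u) whenever anyone starts the IS plan and is not vaccinated, and the protocol expects such cases. SAE and COVID-19 percentages are pulled the same way to the extent that the unvaccinated contribute no such events. For u = 1 to 7 with V = 60, an assumed 70% becomes 68.9% to 62.7%. Both u and the 70% are assumptions. The 20% in Protocol 13.7 refers to missing Week 4 antibody data and cannot stand in for non-vaccination.

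A reader might take it that every unvaccinated participant is withdrawn and adds nothing to the safety data. Neither is quite right: unvaccinated rollovers go back to their previous schedule, and Grade 3 or higher unsolicited events are collected before vaccination. Dilution may be unequal between arms, but the documents do not establish which arms are affected more. The change should be made before database lock because it is cheap and the population it needs is already defined.

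**What to change.** In SAP 9.1 and 9.2:

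- Use the vaccinated population of the relevant stage (already in SAP 5) as denominator for every event collected from Day 1.
- For solicited reactions, use vaccinated participants with at least one diary day, and report the number with none by arm.
- Report unsolicited events of Grade 3 or higher before vaccination in a separate table, with plan initiators as denominator. For this table, state in SAP 5 what counts as initiating the plan in the continue arms and in Cohorts C and F, and whether a rescreened person counts once.

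The change is to SAP text and table shells only; no data collection changes. The cost is slightly higher reported rates and one extra denominator to explain.

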9.2.1. Solicited Adverse Events

Participants are provided access to an electronic 7-day diary to aid in recording solicited local and systemic reactions to the vaccine, as well as symptoms of a potential allergic reaction, unsolicited AEs, and concomitant medications, including start and stop dates. The diary includes instructions for participants on how to take an oral temperature and how to measure injection site reactions. A paper copy of the diary may be provided for participants who do not have a device to access the electronic diary or as a backup collection tool. A member of the study team will review the information in the diary with the participant, including how to use and access the electronic diary, and will record adverse events on the CRF page as appropriate based on review of the diary.

Summary displays based on the maximum severity of solicited symptoms reported over the 7-day period will be presented in tables and graphically by study arm. Summaries of the diary entries over the 7-day period will also be presented by study arm.

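### Vaccinated participants without a diary stay in the denominator of the solicited-reaction percentage and dilute it

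*SAP*

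**What the plan says.** **Source of the data.** SAP 9.2 states: "Solicited AEs (all grades) will be collected from Day 1 (vaccine administration) through 7 days post study vaccination using the MyOwnMed vaccine reaction diary". Two routes into EDC are added. A solicited event that is also an SAE or MAAE is entered there, and so is one already reported in the diary that is still ongoing at Day 7. SAP 9.2.1 allows a paper copy of the diary as backup and has staff review the diary with the participant.

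**Denominator.** SAP 9.1: "All safety analyses will be carried out using the safety sample defined in Section 5 unless otherwise noted". SAP 5 says that the safety population "will be defined as all participants who initiate the treatment plan for IS medications or receive an additional dose of vaccine". There is no diary condition, and Section 5 defines no diary-evaluable set. SAP 9.2: "Percentages will be based on the number of subjects in the safety population". The overall summary table in the same section gives the "Total number of events, and number and percentage of subjects experiencing at least one event for the following categories", and solicited adverse events are one of those categories.

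**Missing data.** SAP 9.1: "Missing safety information will not be imputed".

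**Diary displays.** SAP 9.2.1 plans "Summary displays based on the maximum severity of solicited symptoms reported over the 7-day period", by study arm, together with summaries of the diary entries. It states neither a denominator nor a rule for missing days or missing diaries.

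**The concern.** For an ordinary reaction, meaning one that is neither serious nor medically attended, the diary is the only collection route that SAP 9.2 sets out. A vaccinated person who returns no diary cannot appear as a reactor, yet stays in the denominator. No sentence scores that person as reaction-free, but in the overall table the result is the same.

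The maximum-severity displays have a related gap. Someone who completes 2 of the 7 days contributes a two-day maximum that is shown as a seven-day one.

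Adverse event incidence is a secondary objective in both stages (Protocol 2.2), and the 9.2.1 displays are presented by arm. If completion differs between arms, part of any difference in reactogenicity reflects diary return and not the vaccine. Protocol 12.3.2 attributes every solicited event to the vaccine. If diary events are counted there, the dilution therefore also reaches the secondary endpoint of Grade 1 or higher related events (Protocol 3.3).

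**Working it through.** The plan gives no expected reaction rate and no diary-completion rate, so there is no figure to reproduce. The check has four steps.

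**1. Who is counted in the solicited row of the overall table**

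| Vaccinated participant | In denominator | Can enter numerator |
|---|---|---|
| Diary returned | yes | yes |
| No diary, solicited event also an SAE or MAAE | yes | yes, through EDC |
| No diary, ordinary reaction | yes | no |

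The Day 7 route does not help the third row, because it starts from an event already in the diary. The paper copy is the same diary.

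**2. Size if diary absence is independent of reaction**

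Inputs:
- N = 60 vaccinated per arm, the Adult Stage 1 maximum (Protocol 3.1.1.1). It cancels.
- m = share without a diary. It is not in the documents; the assumed range is 5% to 30%.
- p = true rate of any solicited reaction. It is not a planning value in the documents; the assumed range is 50% to 80%.

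Reported rate = p × N(1 − m) / N = p(1 − m).

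For p = 80% and m = 10%: 54 diaries, 0.80 × 54 = 43.2 expected reactors, 43.2 / 60 = 72%. For m = 20%: 48 diaries, 38.4 expected reactors, 38.4 / 60 = 64%.

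| True rate | m = 5% | 10% | 20% | 30% |
|---|---|---|---|---|
| 50% | 47.5% | 45.0% | 40.0% | 35.0% |
| 70% | 66.5% | 63.0% | 56.0% | 49.0% |
| 80% | 76.0% | 72.0% | 64.0% | 56.0% |

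The relative understatement equals m. With diary holders as denominator, the rate is p at every m.

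**3. Unequal completion between arms**

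Take the same true rate of 70%, with 5% missing in one arm and 15% in the other. The reported rates are 0.70 × 0.95 = 66.5% and 0.70 × 0.85 = 59.5%, a spurious gap of 7 percentage points.

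**4. Without independence**

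Let pD be the rate in diary holders and pN the rate in the others, with complete diaries and the EDC route set aside.
- Truth = (1 − m)pD + m·pN.
- Reported = (1 − m)pD, so the shortfall is m·pN. It is never negative.
- Diary-based rate = pD, which exceeds the truth when pN < pD and falls below it when pN > pD.

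At the extreme pN = 0, with pD = 80% and m = 20%, the truth is 64%. The SAP figure is then correct and the diary-based 80% is too high. The direction of the current rule is thus fixed (low or exact), while its size depends on who fails to return a diary.

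**The case against.** The strongest reply is that the plan works hard to prevent missing diaries. Protocol 12.5.1 makes sites responsible for diary completion and for help with entry. A Week 1 diary review is scheduled, there is a paper backup, and Protocol 12.4.3 lists interview and structured questioning among the ways adverse events may be found. With near-complete diaries the bias is negligible. This stands as a limit on size. None of it changes the denominator or says how a missing diary is tabulated.

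A second reply concerns SAP 9.2.1. No denominator is stated there, a maximum over no entries is undefined, and a missing category would fit the text. The planned summaries of diary entries might also show how many participants contributed. This stands too: the safety set applies to those displays only through the general default in SAP 9.1. The explicit conflict is confined to the overall table.

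Third, the safety proportions are descriptive (Protocol 13.4.4), and no test of reactogenicity between vaccines is specified. That lowers the stakes but does not make a diluted percentage right.

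Finally, the SAP is to be updated before database lock (SAP 2), and its contents page lists attachments that are not in the public text. A denominator could be set there. SAP 9.2.1 itself, unlike SAP 9.4 and 9.5, does not defer its details to a later version.

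**Conclusion.** The point holds for the solicited row of the overall table, by the SAP's stated rule, and for the 9.2.1 displays by default. The percentage is too low whenever a vaccinated participant without a diary had an ordinary reaction. Under independence the relative understatement equals the missing share, for example 80% reported as 72% or 64% at 10% or 20% missing. Both the reaction rate and the missing share are assumptions.

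A reader might infer more than the documents support:
- **That the diary is the only window on solicited reactions.** It is not, because those that are also SAEs or MAAEs go into EDC.
- **That the SAP declares non-returners reaction-free.** It does not. The effect follows from the denominator and the absence of imputation.
- **That 20% missing diaries is a planning figure.** Protocol 13.7 allows up to 20% for missing Week 4 antibody data, which is a different variable.
- **That adult versus parent-completed diaries would distort vaccine comparisons.** SAP 5 defines the analysis samples separately by age group, so this does not confound comparisons within an age group.

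The matter is modest and is best settled before lock.

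**What to change.** In SAP 9.2 and 9.2.1:

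1. Use as denominator for solicited events the vaccinated participants with at least one completed diary day, and also count anyone with a solicited event recorded in EDC.
2. Define a completed day as one with any symptom rating or a ticked No Symptoms box, and treat that tick as zero for every listed symptom on that day. This matters because the diary cards (Protocol 20.3 to 20.6) tell symptom-free participants to tick the box and leave the rest blank. A denominator that required an entry for each symptom would drop these true zeros and inflate the rates.
3. Report the numbers with no, partial and complete diaries by arm.
4. Add a sensitivity display of maximum severity in participants with a complete diary, which deals with the partial-week problem.
5. Keep the safety-population percentage as a second display.

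The cost is SAP wording, a few count rows and two extra displays, with no new data collection. Denominators will differ from those of other safety tables. The new rate may be somewhat high if symptom-free participants return fewer diaries, and participants added only through EDC push it the same way. In that case the two displays bracket the true rate. They would not if non-returners reacted more often than returners, so the completion counts belong beside them.
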